## **9.4 Cardiovascular Assessment**

### **9.4.1 Cardiovascular Analysis**

The primary parameters for the cardiovascular analyses will be mean hourly HR, mean hourly HR nadirs, and HR. Mean hourly HR from 1 hour predose to 12 hours postdose will be calculated on Days -1, 1, 8, and 9 from the Holter monitoring data. Negative chronotropic effects will be evaluated using nadir (1–6 h), nadir (>6 h–12 h), and nadir (1–12 h), which are defined as the lowest mean hourly HR during each postdose time period on each day. The parameters HR and PR interval will also be determined on Days -1, 1, 8, and 9 from the 10-second Holter traces extracted at the time points listed in Section 2 of the protocol. Orthostatic changes in blood pressure and pulse rate will be determined at the time points listed in Section 2 of the protocol.

### **9.4.2 Cardiovascular Statistical Methodology**

Cardiovascular parameters will be evaluated to determine the impact of coadministration of propranolol with lasmiditan on HR, PR interval, and blood pressure compared to propranolol alone. Primary cardiovascular parameters (mean hourly HR, mean hourly HR nadirs, and HR) will be evaluated in a linear mixed-effects model with a fixed effect for treatment (lasmiditan coadministered with propranolol [Day 9; test treatment] versus propranolol alone [Day 8; reference treatment]), and a random effect for subject. Least squares means will be calculated for the test and reference treatments. Mean treatment differences will be presented, along with the corresponding 90% CI.

An example of the SAS code that will be used is as follows:

```
proc mixed data=xxx;
  class trtmnt subject;
  model cardio = trtmnt / alpha=0.1;
  random subject;
  lsmeans trtmnt / pdiff;
run;
```

where cardio is the cardiovascular primary parameter.

Primary cardiovascular parameters may be log-transformed prior to the statistical analysis if a review of the data indicates that the assumption of normality is violated.

A similar analysis will be performed to determine the impact of coadministration of lasmiditan with propranolol on HR, PR interval, and blood pressure compared to lasmiditan alone. The model will include the following treatments: propranolol coadministered with lasmiditan (Day 9; test treatment) versus lasmiditan alone (Day 1; reference treatment). The impact of coadministration of propranolol with lasmiditan on orthostatic blood pressure and pulse rate will be evaluated using descriptive statistics as appropriate.

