## 7. SAMPLE SIZE JUSTIFICATION

Up to 44 subjects may be enrolled to ensure 36 subjects complete the study. Assuming a standard deviation for the change in HR of 10.9 (based on previous studies [H8H-MC-CD-LAHO and H8H-CD-LAHJ]), this will result in a 90% probability that the half-width of the 90% confidence interval (CI) about the mean within-subject change is no larger than 5 beats per minute (bpm). Subjects who are randomized but do not complete the study may be replaced to ensure that enough subjects complete the study.

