#### **9.5.7 Holter Ambulatory Monitoring**

Continuous 12-lead Holter recordings over 12 hours will be performed. Mean hourly HR and mean hourly HR nadirs will be calculated. Data will be summarized by treatment together with changes from baseline, and listed. For ECG extractions baseline is defined as the mean of the last triplicate extractions taken predose. For the mean hourly HR, baseline is defined as the hourly mean of the one hour predose time point.

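### Does the primary heart-rate model in SAP 9.4.2 need a time term or a by-time statement because hourly and extracted heart rates have several values per subject-day?

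*SAP*

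**What the plan says.** SAP section 9.4.1 lists the parameters: "The primary parameters for the cardiovascular analyses will be mean hourly HR, mean hourly HR nadirs, and HR". They differ in how many values each subject contributes per day.

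- **Hourly means.** "Mean hourly HR from 1 hour predose to 12 hours postdose will be calculated on Days -1, 1, 8, and 9", which gives one predose and 12 postdose values per subject-day.
- **Nadirs.** There are three windows, "which are defined as the lowest mean hourly HR during each postdose time period on each day", so each window gives one value per subject-day.
- **Extracted heart rate.** "The parameters HR and PR interval will also be determined on Days -1, 1, 8, and 9 from the 10-second Holter traces", at several time points that the SAP leaves to the protocol.

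Section 9.4.2 then sends all of them through one model: "Primary cardiovascular parameters (mean hourly HR, mean hourly HR nadirs, and HR) will be evaluated in a linear mixed-effects model". The primary contrast is Day 9 (combination) against Day 8 (propranolol alone). The example code has treatment and subject as class variables, a random subject effect, and the statement "model cardio = trtmnt / alpha=0.1". It contains no time variable, BY statement or REPEATED statement.

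Two other places bear on the reading. Section 7 sizes the trial on the 90% confidence interval for a mean within-subject change. Section 9.5.7 gives the predose hour its own role: "For the mean hourly HR, baseline is defined as the hourly mean of the one hour predose time point".

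**The concern.** A model with treatment and a random subject intercept is a paired comparison when each subject has one value per day. Applied to a dataset holding every hour of both days, it treats the 12 hours within a day as independent once the subject effect is removed. Heart rate within a day is unlikely to behave that way. Anything that shifts a subject's whole day would be counted 12 times, the error degrees of freedom would rise from 35 to several hundred, and the interval for the primary contrast would normally be too narrow.

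The quantity estimated would change too, from an effect at each hour to an average over hours. Since the primary result is a difference with its 90% interval, leaving that choice open looks serious at first sight.

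**Working it through.** **1. The plan's own precision figure.** Inputs from section 7: 36 completers, SD 10.9 bpm, 90% interval, half-width at most 5 bpm, stated probability 90%. With one change per subject, the half-width is t × s/√36, where t(0.95, 35) = 1.690. The probability that it is at most 5 is P[χ²(35) ≤ 35 × (5 × 6/(t × σ))²].

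- If 10.9 is the SD of a single-day value within subject, σ = 10.9 × √2 = 15.41. The argument is 35 × (30/(1.690 × 15.41))² = 46.4 and the probability is 0.906. The half-width at that SD is 1.690 × 15.41/6 = 4.34 bpm.
- If 10.9 is already the SD of the paired change, the argument is 92.9 and the probability exceeds 0.999. The half-width is 1.690 × 10.9/6 = 3.07 bpm.

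The first version reproduces the stated figure. Both use one change per subject, so neither describes a pooled fit.

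**2. The stated model at one time point.** With 36 complete pairs and one value per subject-day, the error degrees of freedom are 2 × 36 × 1 − 36 − 1 = 35, those of a paired t analysis. The Cardiovascular population in section 8 requires both the test and the reference measurement, so pairs are complete. In simulation, coverage of the nominal 90% interval was 89% to 91% in every setting tried.

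**3. The same model if hours were pooled.** The SAP gives no variance components, so these are assumptions: 12 postdose hours, within-subject variance of an hourly value V = 10.9² = 118.81, and a share ρ of V common to one subject-day. Error degrees of freedom are 2 × 36 × 12 − 37 = 827, or 2 × 36 × 13 − 37 = 899 if the predose hour is included. For ρ = 0.5 and 12 hours:

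- True variance of the mean difference: 2 × (59.405 + 59.405/12)/36 = 3.575, so its SD is 1.891.
- Expected residual mean square: [792 × 59.405 + 35 × 12 × (59.405 + 59.405/12)]/827 = 89.57.
- Pooled half-width: 1.647 × √(2 × 89.57/432) = 1.06 bpm. A paired analysis of daily means would give 1.690 × 1.891 = 3.19 bpm.
- Coverage: P(|Z| < 1.06/1.891) = about 43%.

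Simulated coverage of the pooled interval (4,000 trials per setting, subject SD 8), by ρ and by the SD of an hourly profile shared by all subjects:

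| Profile SD (bpm) | ρ = 0 | 0.1 | 0.3 | 0.5 |
|---|---|---|---|---|
| 0 | 90% | 74% | 56% | 44% |
| 8 | 96% | 84% | 65% | 55% |
| 12 | 99% | 92% | 76% | 64% |

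Pooling would therefore usually give too narrow an interval, and too wide a one where within-day correlation is slight and the profile strong.

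**4. Does the SAP call for pooling?** Three places in the SAP help to answer this.

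- Section 9.3.2 gives a code block of the same form for the pharmacokinetic parameters, with one unindexed response and no BY statement. It serves Cmax and two AUCs for lasmiditan and its metabolites, and nobody would put those into one fit.
- In section 9.4.2 the same block serves three nadir windows, again with no BY statement. Those are plainly separate fits.
- Section 9.5.7 makes the predose hour the baseline for the hourly means, which sits badly with treating it as one more postdose response.

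The missing BY statement is thus how this SAP writes example code throughout. It is no sign that hours are pooled.

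**The case for a change.** The strongest case for a change is that choosing the primary model is the SAP's own task, and section 3 says the SAP supersedes the protocol's statistical considerations. The example code was plainly carried over from the pharmacokinetic section, where each parameter has one value per treatment, and was not adapted to serial data. Nothing in 9.4.2 says whether the fit is by hour, on a daily mean or on all hours together. One sentence would settle it at almost no cost.

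Much of that is fair. The wording is incomplete, and section 7 does not settle the choice alone: a nadir or a daily mean also gives one difference per subject and can meet the 5 bpm bound. But the damage arises only under pooling, which the SAP does not state and its code convention does not suggest. The coverage losses rest on assumed correlations and range from severe to none. Section 3 also places the detailed output in a separate shell document, not at hand, which would ordinarily show whether estimates are tabulated by time point. A repeated-measures model with time and treatment-by-time terms is a reasonable alternative, but a preference; the by-time paired analysis is already valid.

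**Conclusion.** No change is called for. Section 9.4.2 omits a detail that analysts would fill in the sensible way: fit the stated model at each postdose time point and for each nadir window, with the predose hour as baseline. On that reading the primary interval has about 90% coverage, with a half-width near 4.3 bpm if 10.9 is a single-day within-subject SD, or near 3.1 bpm if it is the SD of the change. Both are within the 5 bpm target.

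Coverage of about 43% at ρ = 0.5 with no hourly profile belongs only to a pooled fit under assumed variance components. The conclusion rests on reading the code block as a one-parameter template, which its other uses in the SAP support. It would change if the output shells showed a single pooled estimate over hours from this model.

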### **4. STUDY OBJECTIVES**

#### **4.1 Primary Objective**

The primary objective of this study is to evaluate the effects of propranolol alone and in combination with lasmiditan on heart rate (HR).

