#### **4.2 Secondary Objectives**

The secondary objectives of this study are:

- To evaluate the effects of propranolol alone and in combination with lasmiditan on blood pressure and PR interval.
- To explore the tolerability of a single dose of lasmiditan alone or in combination with propranolol.
- To evaluate the PK of lasmiditan alone and in combination with propranolol.
- To evaluate the PK of propranolol alone and in combination with lasmiditan.

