### **5. STUDY DESIGN**

This is an open-label, fixed-sequence study in healthy subjects to assess the cardiovascular effects of coadministration of lasmiditan with propranolol.

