#### Dosing Period:

Subjects will be admitted to the clinical research unit (CRU) on Day -2. On Day 1, subjects will receive a single dose of 200 mg lasmiditan, then receive propranolol (immediate release formulation; half-life approximately 3 to 6 hours) 80 mg twice daily (bid) on Days 4 through 10 and a single dose of 200 mg lasmiditan coadministered with propranolol on Day 9. Subjects will reside in the CRU from Day -2 until Day 11 when they may be discharged from the CRU following completion of all study procedures, at the investigator's discretion.

Study governance considerations are described in detail in Appendix 3 of the protocol.

Blood samples will be collected predose and up to 48 hours postdose on Days 1 and 9 for the measurement of plasma concentrations of lasmiditan and its metabolites. Blood samples will also be collected predose and up to 12 hours postdose on Days 8 and 9 for the measurement of plasma concentrations of propranolol.

[figure not shown]
Safety assessments performed during the study will include adverse events (AEs), clinical laboratory evaluations, vital signs measurements, 12-lead ECGs, and physical examinations.

Cardiovascular effects will be assessed by Holter ambulatory monitoring and replicate measurements of blood pressure at predose, and for 12 hours postdose on Days -1, 1, 8, and 9.

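### SAP 9.4.2 contrasts only on-drug days, so the effects of propranolol alone named in 4.1 and 4.2 get no estimate against no drug, although a drug-free Day -1 profile is collected

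*SAP*

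**What the plan says.** The primary objective (SAP 4.1) is "to evaluate the effects of propranolol alone and in combination with lasmiditan on heart rate (HR"), and the first secondary objective (4.2) is "To evaluate the effects of propranolol alone and in combination with lasmiditan on blood pressure and PR interval".

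Section 9.4.2 plans two comparisons in mixed models with treatment fixed and subject random. The first is "lasmiditan coadministered with propranolol [Day 9; test treatment] versus propranolol alone [Day 8; reference treatment". For the second: "The model will include the following treatments: propranolol coadministered with lasmiditan (Day 9; test treatment) versus lasmiditan alone (Day 1; reference treatment". It adds: "Least squares means will be calculated for the test and reference treatments". The sentence that sets up the first model names only the primary HR parameters.

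Data are collected on a further day. Section 5 (Dosing Period) plans "replicate measurements of blood pressure at predose, and for 12 hours postdose on Days -1, 1, 8, and 9", alongside Holter monitoring. Section 9.4.1 says: "Mean hourly HR from 1 hour predose to 12 hours postdose will be calculated on Days -1, 1, 8, and 9". It has extracted HR and PR interval determined on the same four days. Lasmiditan on Day 1 is the first study drug and propranolol starts on Day 4, so Day -1 is drug-free.

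The treatment list in section 6 has three entries, all on drug. For vital signs, 9.5.5 takes as baseline a Day 1 predose value, defined separately for each treatment period. For Holter data, 9.5.7 takes the last predose triplicate (ECG extractions) or the hour before dosing (mean hourly HR), and names no day.

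**The concern.** An effect of propranolol alone is a difference between propranolol and no propranolol, with no lasmiditan on either side. Neither planned contrast gives that. Day 9 versus Day 8 estimates what lasmiditan adds to propranolol. Day 9 versus Day 1 estimates what propranolol adds to lasmiditan.

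If the objectives mean what they literally say, half of the primary objective and half of a secondary objective end without an estimate against no drug and without a confidence interval, although the required data are collected. The combination also gets no modelled difference from no drug. Choosing a reference for propranolol alone after the data are seen would be a post-hoc choice for the primary endpoint.

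**Working it through.** **1. Which days enter the models.** Profiles exist on Days -1, 1, 8 and 9. The contrasts in 9.4.2 use {9, 8} and {9, 1}. Day -1, the only full drug-free profile, is in neither: 0 of 2 contrasts have a drug-free reference.

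**2. Can Day 9 minus Day 1 stand in for the propranolol-alone effect?** Write D for the mean on a given day.

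- Propranolol added to lasmiditan: D9 − D1
- Propranolol alone: D8 − D(-1)
- Their difference: (D9 − D1) − (D8 − D(-1)) = (D9 − D8) − (D1 − D(-1))

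The right-hand side is the lasmiditan effect on top of propranolol minus the lasmiditan effect alone. The two propranolol effects agree only if that is zero. Checking it requires D(-1), which no planned contrast contains.

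**3. Can the descriptive tables stand in?**

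- Holter HR and PR interval (9.5.7): no baseline day is named. If it is predose on the same day, the Day 8 baseline follows Days 4 to 7 twice daily = 4 × 2 = 8 propranolol doses, and the Day 9 baseline follows 5 × 2 = 10. The change from baseline would then remove much of the effect sought. If it means before the first study dose, the change is against a drug-free value.
- Blood pressure and pulse rate (9.5.5): the SAP defines no treatment periods, so the day is unclear. If study Day 1 is meant, Day 8 does get a drug-free descriptive change, but against a predose reading that is not time-matched over 12 hours and with no planned interval.

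**4. The plan's own precision figure (section 7).** Inputs: 36 completers, SD 10.9, and 90% probability that the 90% CI half-width is at most 5 bpm.

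- Half-width: h = t(0.95, 35) × SD / √36, with t = 1.6896.
- Probability: P(h ≤ 5) is the chi-square distribution function on 35 df at 35 × (5/h)², with h taken at the planning SD.
- SD 10.9 × √2 = 15.415 (10.9 as the SD for one day, days uncorrelated): h = 1.6896 × 15.415 / 6 = 4.34 bpm; P = 0.906; smallest n = 36. The stated figure is reproduced.
- SD 10.9 taken as the SD of the difference itself: h = 1.6896 × 10.9 / 6 = 3.07 bpm; P > 0.999; n = 21 would suffice.

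Section 7 calls 10.9 the SD of the change, yet its figure is reproduced only with the √2 factor. That is a separate matter; here it just sets the range.

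**5. Precision of an added contrast.** If the same SD applies to Day 8 or Day 9 minus Day -1 (an assumption), the half-width with 36 completers is 3.07 to 4.34 bpm, inside the 5 bpm target. No extra subjects are needed for HR.

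**6. Spacing.** With no Day 0, Day -1 to Day 8 is 8 days, the same as Day 1 to Day 9 in the planned contrast; Day -1 to Day 9 is 9 days.

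**The case against.** The strongest reply is that propranolol alone is meant only as the comparator. Section 5 gives the purpose of the study as "to assess the cardiovascular effects of coadministration of lasmiditan with propranolol", and 9.4.2 opens by comparing the combination with propranolol alone. The pharmacokinetic objectives in 4.2 use the same form of words, and 9.3.2 serves each with combination versus alone. This reading is tenable. The pharmacokinetic parallel supports it without proving it, since exposure needs no drug-free reference. A reader might infer from 4.1 that the primary objective is left unanswered; the documents do not support that, because the combination part is served by Day 9 versus Day 8 and the rest depends on which reading is meant. Even so, the comparator reading leaves 4.1 and 4.2 loosely worded and the Day -1 profile without a stated purpose.

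A second reply is that the protocol or the table shells, neither of them shown, may give Day -1 a role. They may describe it. But section 3 says the SAP supersedes the protocol's statistical considerations, and 9.1 restricts summaries and analyses to those the SAP details. Day -1 data would be listed under 9.1, but a listing gives no estimate.

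A third is that in a fixed sequence Day 8 minus Day -1 carries time and confinement effects. That is true and should be stated. The planned Day 9 versus Day 1 contrast has the same limit over the same 8 days.

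Two further inferences go too far. One is that Holter HR, nadirs and PR interval certainly get no drug-free change: 9.5.7 names no day, and 9.5.3 shows that a baseline before Day 1 dosing is used elsewhere in this SAP. The other is that blood pressure and PR interval certainly get a Day 8 least squares mean: 9.4.2 makes this explicit only for the HR parameters.

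**Conclusion.** The point holds in conditional form. On the plain wording of 4.1 and 4.2, the plan gives no modelled effect of propranolol alone on HR, blood pressure or PR interval. It gives at most a Day 8 level, and Day 9 minus Day 1 is a substitute only under an equality that the planned contrasts cannot check. The drug-free Day -1 profile has no stated contrast or baseline role, and the descriptive tables do not reliably make up for it.

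The size of the missing effect cannot be determined from the SAP. The 3.1 to 4.3 bpm half-widths describe the precision of the proposed HR contrast, not the size of the defect, and rest on the planning SD carrying over. The planned Day 9 versus Day 8 and Day 9 versus Day 1 contrasts are unaffected. This should be corrected before SAP sign-off; confidence is medium because the objectives allow two readings.

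**What to change.** - **9.4.2:** add Day -1 as a no-drug reference in a model of the same form. Report time-matched Day 8 minus Day -1 (propranolol alone) and Day 9 minus Day -1 (combination) differences with 90% CIs for HR including nadirs, PR interval and blood pressure. State that in a fixed sequence these also carry time and confinement effects. Day 1 minus Day -1 is optional.
- **9.5.5 and 9.5.7:** name the baseline study day and make it a drug-free one. Day -1 and Day 1 predose both qualify; Day -1 is not the only defensible choice.
- **If only the comparator reading is intended:** say so in 4.1, 4.2 and 9.4.2, and state what the Day -1 profile is for.

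The cost is SAP wording, a few extra contrasts and some table columns. No new data or procedures are needed. Section 3 requires sign-off before the first subject is dosed, so a change made by then is prespecified.

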**Figure 1. Illustration of study design for Protocol H8H-MC-LAHD**

## 6. TREATMENTS

The treatment sequence to be administered to all subjects is: 200 mg lasmiditan (Day 1); 80 mg propranolol bid (Day 4 to Day 10); 200 mg lasmiditan + 80 mg propranolol (Day 9).

The following is a list of the study treatments that will be used in the TFLs.

Study Treatment Name	Treatment order in TFL
200 mg lasmiditan	1
80 mg propranolol bid	2
80 mg propranolol bid + 200 mg lasmiditan	3

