#### **9.3.2 Pharmacokinetic Statistical Methodology**

Pharmacokinetic parameters will be evaluated to determine the impact of propranolol coadministration on the PK of a single dose of lasmiditan and its metabolites. Log-transformed  $C_{\max}$ ,  $AUC(0-\infty)$ , and  $AUC(0-t_{last})$  parameters will be evaluated in a linear mixed-effects model with a fixed effect for treatment (lasmiditan coadministered with propranolol [Day 9; test treatment] versus lasmiditan alone [Day 1; reference treatment]), and a random effect for subject. The treatment differences will be back-transformed to present the ratios of geometric means and the corresponding 90% CI.

An example of the SAS code that will be used is as follows:

```
proc mixed data=xxx;
  class trtmnt subject;
  model l_pk = trtmnt / alpha=0.1;
  random subject;
  lsmeans trtmnt / pdiff;
run;
```

where l\_pk is the log-transformed (base e) PK parameter.

The  $t_{max}$  will be analyzed using a Wilcoxon signed rank test. Estimates of the median difference based on the observed medians, 90% CIs and p-values from the Wilcoxon test will be calculated.

A similar analysis will be performed to determine the impact of coadministration of a single dose of lasmiditan on the steady-state PK of propranolol. The model will include the following treatments: propranolol coadministered with lasmiditan (Day 9; test treatment) versus propranolol alone (Day 8; reference treatment).

Additional analyses may be performed, as warranted.

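### Does the missing interval option in the example SAS code put the planned 90% confidence intervals at risk?

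*SAP*

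**What the plan says.** For the primary heart rate parameters, SAP section 9.4.2 specifies a mixed model with a fixed treatment effect and a random subject effect. It compares Day 9 (combination, test) with Day 8 (propranolol alone, reference). The output is stated in words: "Mean treatment differences will be presented, along with the corresponding 90% CI". A similar comparison of Day 9 with Day 1 (lasmiditan alone) follows.

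Section 9.3.2 does the same for lasmiditan PK on the log scale, Day 9 against Day 1: "The treatment differences will be back-transformed to present the ratios of geometric means and the corresponding 90% CI". Propranolol PK is handled similarly, Day 9 against Day 8.

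Each section then shows a short code block. In 9.4.2 it is introduced by "An example of the SAS code that will be used is as follows". The level appears on the MODEL statement ("model cardio = trtmnt / alpha=0.1" in 9.4.2, "model l_pk = trtmnt / alpha=0.1" in 9.3.2), and the contrast comes from "lsmeans trtmnt / pdiff". Neither block has a `CL` option, an `ALPHA=` on LSMEANS, or an ESTIMATE statement. Section 7 also uses the 90% level: it sizes the trial on the half-width of a 90% interval for the within-subject change in heart rate.

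**The concern.** In PROC MIXED the `ALPHA=` option on MODEL sets the level for intervals on the fixed-effect parameter estimates. LSMEANS takes its own `ALPHA=` and does not inherit the one on MODEL. `PDIFF` without `CL` gives no limits at all. Run as printed, the code would therefore not produce the interval that is the main inferential output for the primary heart rate parameters and for PK.

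Two further worries follow. The quickest repair, adding `CL` alone, would give the default 95% limits, which look plausible in a table. And `PDIFF` without a named control subtracts later class levels from earlier ones. If the treatment variable follows the list in section 6 (the column headed "Treatment order in TFL"), the combination comes last and the printed contrast is reference minus test, the reverse of the prose. If either slipped through, the reported interval would have the wrong level or the wrong sign.

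**Working it through.** The statements about SAS rest on standard PROC MIXED behaviour; the code was not executed.

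**1. Can the promised interval be obtained from the printed output?** The Cardiovascular population (section 8) requires both test and reference measurements, so the data are complete pairs. With n = 36 completers (section 7) the contrast has 36 − 1 = 35 degrees of freedom. The code prints the difference d, its standard error SE and the df. The 90% limits are

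d ± t(0.95, 35) × SE, with t(0.95, 35) = 1.690.

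For PK the same limits are exponentiated. Nothing needs to be refitted. The estimate, SE, df and p-value do not depend on the confidence level.

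**2. What would `CL` without a level do?** t(0.975, 35) = 2.030, and 2.030 / 1.690 = 1.20, so the limits are 20% wider. With the section 7 SD of 10.9 bpm taken, as that section describes it, as the SD of the change:

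- 90%: 1.690 × 10.9 / √36 = 3.07 bpm
- 95%: 2.030 × 10.9 / √36 = 3.69 bpm

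**3. The section 7 precision statement.** Section 7 claims a 90% probability that the 90% half-width is at most 5 bpm. With S the sample SD of the change and σ its true value, (n − 1)S²/σ² is chi-square on n − 1 df, so

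P(half-width ≤ 5) = P(χ²₃₅ ≤ 35 × [5 × 6 / (t × σ)]²).

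- σ = 10.9, 90% interval: 35 × [30 / (1.690 × 10.9)]² ≈ 92.9; probability above 0.999.
- σ = 10.9 × √2 = 15.41, 90% interval: 35 × [30 / (1.690 × 15.41)]² ≈ 46.4; probability 0.907.
- σ = 15.41, 95% interval: 35 × [30 / (2.030 × 15.41)]² ≈ 32.2; probability 0.394, with half-width 2.030 × 15.41 / 6 ≈ 5.22 bpm, against 4.34 bpm at 90%.

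The plan's own 90% is reproduced only if 10.9 is assumed to be a per-day SD. How section 7 labels that SD is a separate matter that the code does not affect. What counts here is that section 7 was computed at the 90% level, in agreement with the prose of 9.3.2 and 9.4.2.

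**4. Direction.** The SAP does not say how the treatment variable is coded in the model. If the combination is the last level, the printed heart rate difference has the opposite sign and a PK ratio of 1.25 prints as 1/1.25 = 0.80. Both are exact reversals of the same result: change the sign, or invert, and swap the limits.

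**5. Text and code side by side.** The prose gives level, contrast, test day and reference day. The code gives the model and omits the options that format the output. They disagree on no estimand, model term or level; the 0.1 in the code also points to 90%.

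**The case for a change.** The strongest case for acting is that the code is presented as what will be used, and section 3 makes the finalised SAP and table shells the template for the study report. The code evidently intends the 0.1 to deliver the 90% interval, and it does not. The repair is one line in two places, and it would remove a foreseeable slip. On direction, both natural codings from section 6, the numeric order and the alphabetical order of the treatment names, put the combination last, so a reversed contrast is likely from the code as printed.

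The mismatch is real and the description of the software is sound, so that part stands. It does not show that the plan leaves anything open. The level is stated in words in both sections and implied again by section 7. Test and reference are named by treatment and day. The blocks are labelled as examples and use a placeholder data set name. An absent interval is noticed as soon as a table column has nothing to fill it. A 95% interval or a reversed contrast would contradict the SAP's text and would be an error of execution. The column in section 6 is a display order, not a coding rule. The 5.22 bpm half-width needs both that error and a reading of 10.9 that differs from section 7's own description.

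**Conclusion.** The example code is incomplete: as printed it gives no confidence limits for the treatment contrast, in either section. This is a clerical slip in illustrative code. The governing prose fixes the 90% level and the test-versus-reference direction, and the 90% limits follow by arithmetic from the printed estimate, standard error and degrees of freedom. The effect on planned results is nil. The 20% widening (3.07 to 3.69 bpm at the stated SD) and the sign reversal arise only if a programmer departs from the text. This rests on standard PROC MIXED behaviour and on analysts treating the prose as binding over the example. Completing the line would be tidying, with no gain in what is estimated or reported, so no change to the plan is needed.
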